7.2. Participant Discontinuation/Withdrawal From the Study

A participant may withdraw from the study at any time at their own request. Reasons for discontinuation from the study include the following:

- Refused further study procedures;
- Lost to follow-up;
- Death;
- Study terminated by sponsor.

At the time of discontinuing from the study, if possible, an early discontinuation visit should be conducted. See the SoA for assessments to be collected at the time of study discontinuation and follow-up and for any further evaluations that need to be completed.

The early discontinuation visit applies only to participants who are enrolled/randomized and then are prematurely withdrawn from the study. Participants should be questioned regarding their reason for withdrawal.

If a participant withdraws from the study, they may request destruction of any remaining samples taken and not tested, and the investigator must document any such requests in the site study records and notify the sponsor accordingly.

If the participant withdraws from the study and also withdraws consent (see Section 7.2.1) for disclosure of future information, no further evaluations will be performed and no additional data will be collected. The sponsor may retain and continue to use any data collected before such withdrawal of consent.

7.2.1. Withdrawal of Consent

Participants who request to discontinue receipt of study intervention will remain in the study and must continue to be followed for protocol-specified follow-up procedures. The only exception to this is when a participant specifically withdraws consent for any further contact with them or persons previously authorized by the participant to provide this information. Participants should notify the investigator in writing of the decision to withdraw consent from future follow-up, whenever possible. The withdrawal of consent should be explained in detail in the medical records by the investigator, as to whether the withdrawal is only from further receipt of study intervention or also from study procedures and/or posttreatment study follow-up, and entered on the appropriate CRF page. In the event that vital status (whether the participant is alive or dead) is being measured, publicly available information should be used to determine vital status only as appropriately directed in accordance with local law.

7.3. Lost to Follow-up

A participant will be considered lost to follow-up if the participant repeatedly fails to return for scheduled visits and is unable to be contacted by the study site.

The following actions must be taken if a participant fails to attend a required study visit:

- The site must attempt to contact the participant and reschedule the missed visit as soon as possible. Counsel the participant on the importance of maintaining the assigned visit schedule and ascertain whether the participant wishes to and/or should continue in the study;
- Before a participant is deemed lost to follow-up, the investigator or designee must
 make every effort to regain contact with the participant (where possible, 3 telephone
 calls and, if necessary, a certified letter to the participant's last known mailing
 address or local equivalent methods). These contact attempts should be documented
 in the participant's medical record;
- Should the participant continue to be unreachable, the participant will be considered
 to have withdrawn from the study.

8. STUDY ASSESSMENTS AND PROCEDURES

8.1. Administrative Procedures

The investigator (or an appropriate delegate at the investigator site) must obtain a signed and dated ICD before performing any study-specific procedures.

Study procedures and their timing are summarized in the SoA. Protocol waivers or exemptions are not allowed.

Adherence to the study design requirements, including those specified in the SoA, is essential and required for study conduct.

All screening evaluations must be completed and reviewed to confirm that potential participants meet all eligibility criteria. The investigator will maintain a screening log to record details of all participants screened and to confirm eligibility or record reasons for screening failure, as applicable.

Participants will be screened within 35 days prior to administration of the study intervention to confirm that they meet the study population criteria for the study. If the time between screening and dosing exceeds 35 days as a result of unexpected delays (eg, delayed drug shipment), then participants do not require recollection of banked biospecimens.

A participant who qualified for this protocol but did not enroll from an earlier cohort/group may be used in a subsequent cohort/group without rescreening, provided laboratory results obtained prior to the first dose administration meet eligibility criteria for this study. In addition, other clinical assessments or specimen collections, eg, retained research samples, may be used without repeat collection, as appropriate.

Every effort should be made to ensure that protocol-required tests and procedures are completed as described. However, it is anticipated that from time to time there may be circumstances outside the control of the investigator that make it unfeasible to perform the test. In these cases, the investigator must take all steps necessary to ensure the safety and well-being of the participant. When a protocol-required test cannot be performed, the investigator will document the reason for the missed test and any corrective and preventive actions that they have taken to ensure that required processes are adhered to as soon as possible. The study team must be informed of these incidents in a timely manner.

Safety/laboratory/analyte results that have been collected for the purposes of this study and could unblind the study will not be reported to investigative sites or other blinded personnel until the study has been unblinded.

If an IV catheter is utilized for blood sample collections, ECGs and vital sign assessments (pulse rate and BP) should be collected prior to the insertion of the catheter.

For samples being collected and shipped, detailed collection, processing, storage, and shipment instructions and contact information will be provided to the investigator site prior to initiation of the study.

The total blood sampling volume for individual participants in this study is approximately 675 to 870 mL. The actual collection times of blood sampling may change. Additional blood samples may be taken for safety assessments at times specified by Pfizer, provided the total volume taken during the study does not exceed 550 mL during any period of 56 consecutive days.

To prepare for study participation, participants will be instructed on the information in the Lifestyle Considerations and Concomitant Therapy sections of the protocol.

8.1.1. Telehealth Visits

Telehealth visits may be used to assess participant safety and collect data points (see SoA notes). Telehealth includes the exchange of healthcare information and services via telecommunication technologies (eg, audio, video, videoconferencing software) remotely, allowing the participant and the investigator to communicate on aspects of clinical care, including medical advice, reminders, education, and safety monitoring. The following assessments must be performed during a telehealth visit (see the SoA):

- Review and record any AEs and SAEs since the last contact. Refer to Section 8.4.
- Review and record any new concomitant medications or changes in concomitant medications since the last contact.
- Review and record contraceptive method and results of pregnancy testing. Confirm
 that the participant is adhering to the contraception method(s) required in the
 protocol. Refer to Appendix 4.

Study participants must be reminded to promptly notify site staff about any change in their health status.

8.1.2. Home Health Visits

A home health care service may be utilized to facilitate scheduled visits. Home health visits include a healthcare provider conducting an in-person study visit at the participant's location, rather than an in-person study visit at the site. The following may be performed during a home health visit (see the SoA):

- Review and record any AEs and SAEs since the last contact. Refer to Section 8.4.
- Review and record any new concomitant medications or changes in concomitant medications since the last contact.
- Review and record contraceptive method and results of pregnancy testing. Confirm
 that the participant is adhering to the contraception method(s) required in the
 protocol. Refer to Appendix 4.
- Perform physical examination, vital signs, weight, and ECG collection as required by SoA.
- Blood and/or urine sample collection as required by SoA which may include but not limited to:
 - Safety laboratory samples;
 - PK and immunogenicity samples;
 - Exploratory biomarker samples;

- Pregnancy testing;
- Retained research samples.

Study participants must be reminded to promptly notify site staff about any change in their health status.

It is recommended that the investigator discuss temporary or permanent discontinuation of study intervention with the study medical monitor.

8.2. Efficacy Assessments

As this is a healthy participant study, efficacy assessments are not applicable.

8.3. Safety Assessments

Planned time points for all safety assessments are provided in the SoA. Unscheduled safety measurements may be obtained at any time during the study to assess any perceived safety issues.

8.3.1. Physical Examinations

A complete physical examination will include, at a minimum, head, ears, eyes, nose, mouth, skin, heart and lung examinations, lymph nodes, and gastrointestinal, musculoskeletal, and neurological systems.

A brief physical examination will include, at a minimum, assessments of general appearance, the respiratory and cardiovascular systems, and participant -reported symptoms.

Physical examinations may be conducted by a physician, trained physician's assistant, or nurse practitioner as acceptable according to local regulation.

Height and weight will also be measured and recorded as per the SoA. For measuring weight, a scale with appropriate range and resolution is used and must be placed on a stable, flat surface. Participants must remove shoes, bulky layers of clothing, and jackets so that only light clothing remains. They must also remove the contents of their pockets and remain still during measurement of weight.

Physical examination findings collected during the study will be considered source data and will not be required to be reported, unless otherwise noted. Any untoward physical examination findings that are identified during the active collection period and meet the definition of an AE or SAE (Appendix 3) must be reported according to the processes in Sections 8.4.1 to 8.4.3.

8.3.2. Vital Signs

8.3.2.1. Blood Pressure and Pulse Rate

Supine BP will be measured as per SoA with the participant's arm supported at the level of the heart, and recorded to the nearest mm Hg after approximately 5 minutes of rest. The same

arm (preferably the dominant arm) will be used throughout the study. BP should not be taken from the arm with an intravenous infusion. Participants should be instructed not to speak during measurements.

If a single measurement is >140 mm Hg systolic and/or >90 mm Hg diastolic, the BP assessment should be repeated two more times (approximately two minutes apart), and the average of the three BP values recorded in the CRF and noted in the source document.

The same properly sized and calibrated BP cuff should be used to measure BP each time. The use of an automated device for measuring BP and pulse rate is acceptable; however, when done manually, pulse rate will be measured in the brachial/radial artery for at least 30 seconds. When the timing of these measurements coincides with a blood collection, BP and pulse rate should be obtained prior to the nominal time of the blood collection.

Additional collection times, or changes to collection times, of BP and pulse rate will be permitted, as necessary, to ensure appropriate collection of safety data.

Any untoward vital sign findings that are identified during the active collection period and meet the definition of an AE or SAE (Appendix 3) must be reported according to the processes in Sections 8.4.1 to 8.4.3.

8.3.2.2. Respiratory Rate

Respiratory rate will be measured after approximately 5 minutes of rest in a supine position by observing and counting the respirations of the participant for 30 seconds and multiplying by 2. When BP is to be taken at the same time, respiration measurement will be done during the 5 minutes of rest and before BP measurement. Post-dose respiratory rate measurements to be done at the investigator's discretion.

8.3.2.3. Temperature

Temperature will be measured by either oral, tympanic, or temporal artery method, it is preferred for the same method to be used consistently throughout the study. No eating, drinking, or smoking is allowed for 15 minutes prior to the measurement.

8.3.3. Electrocardiograms

Standard 12-lead ECGs utilizing limb leads (with a 10-second rhythm strip) should be collected at times specified in the SoA section of this protocol using an ECG machine that automatically calculates the HR and measures PR interval, QT interval, QTcF, and QRS complex. Alternative lead placement methodology using torso leads (eg, Mason-Likar) should not be used given the potential risk of discrepancies with ECGs acquired using standard limb lead placement. All scheduled ECGs should be performed after the participant has rested quietly for at least 5 minutes in a supine position.

Triplicate 12-lead ECGs will be obtained approximately 2 to 4 minutes apart at all time points during clinical confinement; the average of the triplicate ECG measurements collected

at each nominal time point on Day 1 will serve as each participant's time-controlled baseline OTcF value.

To ensure safety of the participants, a qualified individual at the investigator site will make comparisons to baseline measurements. Additional ECG monitoring will occur if a) the mean value from the triplicate measurements for any postdose QTcF interval is increased by ≥60 ms from the baseline and is >450 ms; or b) an absolute QT value is ≥500 ms for any scheduled ECG. If either of these conditions occurs, then a single ECG measurement must be repeated at least hourly until QTcF values from 2 successive ECGs fall below the threshold value that triggered the repeat measurement.

If a) a postdose QTcF interval remains ≥60 ms from the baseline and is >450 ms; or b) an absolute QT value is ≥500 ms for any scheduled ECG for greater than 4 hours (or sooner, at the discretion of the investigator); or c) QTcF value get progressively longer, the participant should undergo continuous ECG monitoring. A cardiologist should be consulted if QTcF values do not return to less than the criteria listed above after 8 hours of monitoring (or sooner, at the discretion of the investigator).

In some cases, it may be appropriate to repeat abnormal ECGs to rule out improper lead placement as contributing to the ECG abnormality. It is important that leads be placed in the same positions each time in order to achieve precise ECG recordings. If a machine-read QTc value is prolonged, as defined above, repeat measurements may not be necessary if a qualified medical provider's interpretation determines that the QTcF values are in the acceptable range.

ECG values of potential clinical concern are listed in Appendix 8.

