 - Significant trauma or major surgery within 1 month of the first dose of study drug.

Prior/Concomitant Therapy:

- 3. Recent exposure to live or attenuated vaccines within 28 days of the screening visit.
- 4. Use of prescription or nonprescription drugs and dietary and herbal supplements within 7 days or 5 half-lives (whichever is longer) prior to the first dose of study intervention. (Refer to Section 6.9 Prior and Concomitant Therapy for additional details).
- Current use of any prohibited concomitant medication(s). Refer to Section 6.9 Prior and Concomitant Therapy.

Prior/Concurrent Clinical Study Experience:

6. Previous administration with an investigational product (drug or vaccine) within 30 days (or as determined by the local requirement) or 5 halflives preceding the first dose of study intervention used in this study (whichever is longer).

Diagnostic Assessments:

7. Screening supine BP ≥140 mm Hg (systolic) or ≥90 mm Hg (diastolic), following at least 5 minutes of supine rest. If BP is ≥140 mm Hg (systolic) or ≥90 mm Hg

- (diastolic), the BP should be repeated 2 more times and the average of the 3 BP values should be used to determine the participant's eligibility.
- 8. Standard 12-lead ECG that demonstrates clinically relevant abnormalities that may affect participant safety or interpretation of study results (eg, QTcF >450 ms, complete LBBB, signs of an acute or indeterminate- age myocardial infarction, ST-T interval changes suggestive of myocardial ischemia, second- or third- degree AV block, or serious bradyarrhythmias or tachyarrhythmias). If the uncorrected QT interval is >450 ms, this interval should be rate-corrected using the Fridericia method only and the resulting QTcF should be used for decision making and reporting. If QTcF exceeds 450 ms, or QRS exceeds 120 ms, the ECG should be repeated twice and the average of the 3 QTcF or QRS values used to determine the participant's eligibility. Computer-interpreted ECGs should be overread by a physician experienced in reading ECGs before excluding a participant.
- Participants with ANY of the following abnormalities in clinical laboratory tests at screening, as assessed by the study-specific laboratory and confirmed by a single repeat test, if deemed necessary:
 - AST or ALT level ≥1.5 × ULN;

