7.1.2. ECG Changes

A participant who meets the bulleted criteria based on the average of triplicate ECG readings will be withdrawn from the study intervention.

- QTcF >500 ms.
- Change from baseline: QTcF >60 ms.

If a clinically significant finding is identified (including, but not limited to, changes from baseline in QTcF after enrollment), the investigator or qualified designee will determine if the participant can continue in the study and if any change in participant management is needed. This review of the ECG printed at the time of collection must be documented. Any new clinically relevant finding should be reported as an AE.

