10.8. Appendix 8: ECG Findings of Potential Clinical Concern

ECG Findings That May Qualify as AEs

- Marked sinus bradycardia (rate <40 bpm) lasting minutes.
- New PR interval prolongation >280 ms.
- New prolongation of QTcF to >480 ms (absolute) or by ≥60 ms from baseline.
- New-onset atrial flutter or fibrillation, with controlled ventricular response rate: ie, rate <120 bpm.
- New-onset type I second-degree (Wenckebach) AV block of >30 seconds' duration.
- Frequent PVCs, triplets, or short intervals (<30 seconds) of consecutive ventricular complexes.

ECG Findings That May Qualify as SAEs

- QTcF prolongation >500 ms.
- New ST-T changes suggestive of myocardial ischemia.
- New-onset LBBB (QRS complex>120 ms).
- New-onset right bundle branch block (QRS complex>120 ms).
- Symptomatic bradycardia.
- Asystole:
 - In awake, symptom-free participants in sinus rhythm, with documented periods of asystole ≥3.0 seconds or any escape rate <40 bpm, or with an escape rhythm that is below the AV node.
 - In awake, symptom-free participants with atrial fibrillation and bradycardia with 1 or more pauses of at least 5 seconds or longer.
 - Atrial flutter or fibrillation, with rapid ventricular response rate: rapid = rate
 >120 bpm.
- Sustained supraventricular tachycardia (rate >120 bpm) ("sustained" = short duration with relevant symptoms or lasting >1 minute).
- Ventricular rhythms >30 seconds' duration, including idioventricular rhythm (HR <40 bpm), accelerated idioventricular rhythm (HR >40 bpm to <100 bpm), and

monomorphic/polymorphic ventricular tachycardia (HR >100 bpm [such as torsades de pointes]).

- Type II second-degree (Mobitz II) AV block.
- Complete (third-degree) heart block.

ECG Findings That Qualify as SAEs

- Change in pattern suggestive of new myocardial infarction.
- Sustained ventricular tachyarrhythmias (>30 seconds' duration).
- Second- or third-degree AV block requiring pacemaker placement.
- Asystolic pauses requiring pacemaker placement.
- Atrial flutter or fibrillation with rapid ventricular response requiring cardioversion.
- Ventricular fibrillation/flutter.
- At the discretion of the investigator, any arrhythmia classified as an adverse experience.

The enumerated list of major events of potential clinical concern are recommended as "alerts" or notifications from the core ECG laboratory to the investigator and Pfizer study team, and not to be considered as all-inclusive of what to be reported as AEs/SAEs.

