EudraCT	European Union Drug Regulating Authorities Clincal Trials		
	(European Clinical Trials Database)		
CI			
Fc	fragment of the immunoglobulin that is encoded by constant (c)		
	genes		
FcγR	Fc gamma receptor		

Abbreviation	Term		
FIH	first-in-human		
FSH	follicle-stimulating hormone		
GCP	Good Clinical Practice		
GGT	gamma-glutamyl transferase		
GLP	Good Laboratory Practice		
HBcAb	hepatitis B core antibody		
HBsAb	hepatitis B surface antibody		
HBsAg	hepatitis B surface antigen		
HCV	hepatitis C virus		
HCVAb	hepatitis C antibody		
HIV	human immunodeficiency virus		
HP	healthy participant(s)		
HR	heart rate		
HRT	hormone replacement therapy		
IB	Investigator's Brochure		
IBD	Inflammatory Bowel Disease		
CCI/IC ₈₀	% or 80% inhibitive concentration		
ICD	informed consent document		
	International Council for Harmonisation of Technical		
ICH	[전 : [[전 : 10] T		
ID	Requirements for Pharmaceuticals for Human Use identification		
IgG1	Immunoglobulin G1		
IL	interleukin		
IMP	investigational medicinal product		
IND	Investigational New Drug		
INF-γ	interferon gamma		
INR	international normalized ratio		
IP	investigational product		
IPAL	Investigational Product Accountability Log		
IPM	investigational product manual		
IRB	Institutional Review Board		
IV	intravenous(ly)		
k _a	first-order absorption rate constant		
COL			
\mathbf{k}_{el}	first-order elimination rate constant		
KDIGO	Kidney Disease Improving Global Outcomes		
LBBB	left bundle branch block		
LFT	liver function test		
LLOQ	lower limit of quantification		
mAb	monoclonal antibody		
MABEL	minimum anticipated biological effect level		
MD/md	multiple doses		
MQI	medically qualified individual		
	medicany quantied individual		

Abbreviation	Term		
MRT	mean residence time		
NA	not applicable		
NAb	neutralizing antibodies		
CCI			
NIMP	non-investigational medicinal product		
NOAEL	no observed adverse effect level		
OTC	over-the-counter		
PD	pharmacodynamic(s)		
PEF	peak expiratory flow		
PK	pharmacokinetic(s)		
PR	pulse rate		
PSSA	Pfizer's Serious Adverse Event Submission Assistant		
PT	prothrombin time		
CCI			
Q	inter-compartmental clearance		
Q2W	every 2 weeks		
Q4W	every 4 weeks		
QTc	corrected QT interval		
QTcF	QTc corrected using Fridericia's formula		
qual	qualitative		
RBC	red blood cell		
RNA	ribonucleic acid		
S1PR	Sphingosine-1-phosphate receptor		
SAD	single ascending dose		
SAE	serious adverse event		
SAP	Statistical Analysis Plan		

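### Protocol 8.3.3 sets one ECG monitoring trigger on uncorrected QT but stops the resulting repeats on QTcF, and a QTcF above 500 ms can leave the repeats unstarted in a narrow band, wider at single-ECG visits

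*Protocol*

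**What the plan says.** Protocol 8.3.3 has two triggers for extra ECG monitoring. Trigger (a) is on QTcF: it fires when "the mean value from the triplicate measurements for any postdose QTcF interval is increased by ≥60 ms from the baseline" and the value also exceeds 450 ms. Trigger (b) is on the uncorrected interval: "an absolute QT value is ≥500 ms for any scheduled ECG". Either one starts repeats at least hourly, which continue "until QTcF values from 2 successive ECGs fall below the threshold value that triggered the repeat measurement".

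The later steps of 8.3.3 mix the measures. Continuous monitoring can be reached by a persisting QTcF rise, by QT of at least 500 ms lasting more than 4 hours, or by progressive QTcF lengthening. The next rule is on QTcF alone: "A cardiologist should be consulted if QTcF values do not return to less than the criteria listed above after 8 hours of monitoring". The closing paragraph lets repeats be waived for a machine-read QTc prolonged under the preceding definitions, although the only absolute 500 ms limit given there is on QT.

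Elsewhere the 500 ms limit is on QTcF. In 7.1.2 it is a withdrawal criterion ("A participant who meets the bulleted criteria based on the average of triplicate ECG readings will be withdrawn from the study intervention"). Appendix 8 lists "QTcF prolongation >500 ms" among findings that may qualify as SAEs. Protocol 9.3.1.1, SAP 6.1.5 and SAP Appendix 1 call QTcF above 500 ms severe. Protocol 9.3.1.1 and SAP 6.1.5 also tabulate uncorrected QT above 500 ms separately.

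During confinement, ECGs are taken in triplicate. At the other visits the schedules of activities call for single ECGs.

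**The concern.** A rule that starts on one measure and stops on another has no clear stopping point. When (b) fires, the triggering threshold is a QT value, and the stop rule asks whether QTcF is below it. QT and QTcF agree only at 60 bpm, so the outcome depends on heart rate in both directions: monitoring can end while the trigger condition persists, and a QTcF that the protocol elsewhere treats as a withdrawal criterion and possible SAE may not start the repeats.

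At stake is a mandatory safety procedure in a first-in-human study in which ECG change is a primary endpoint. Sites following the same text could act differently on the same tracing.

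**Working it through.** The documents give no figure to reproduce. The check is of threshold logic.

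**Inputs**
- Appendix 10 defines QTcF as "QTc corrected using Fridericia's formula". With RR = 60/HR in seconds, QTcF = QT / (60/HR)^(1/3) and QT = QTcF × (60/HR)^(1/3).
- Trigger, stop, withdrawal and Appendix 8 thresholds are as stated in 8.3.3, 7.1.2 and Appendix 8.
- Baseline QTcF is taken as at most 450 ms, from exclusion criterion 8 in 5.2 ("If QTcF exceeds 450 ms, or QRS exceeds 120 ms, the ECG should be repeated twice", with the average deciding eligibility). That is a screening limit; applying it to the Day 1 baseline is an assumption.
- Heart rate at the ECG is not given. The range 40 to 100 bpm was examined; selected rates are shown.

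**Step 1: convert between the measures**

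| HR (bpm) | QTcF when QT = 500 ms | QT when QTcF = 505 ms |
|---|---|---|
| 45 | 454.3 | 555.8 |
| 50 | 470.5 | 536.6 |
| 55 | 485.7 | 519.9 |
| 60 | 500.0 | 505.0 |
| 65 | 513.5 | 491.7 |
| 75 | 538.6 | 468.8 |
| 90 | 572.4 | 441.2 |

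**Step 2: the stop rule after trigger (b)**

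The triggering ECG is already below 500 ms on QTcF when HR < 60 × (500/QT)^3. For QT 500, 510 and 520 ms this gives HR below 60.0, 56.5 and 53.3 bpm. At 50 bpm, QT 500 ms is 500 / 1.2^(1/3) = 470.5 ms on QTcF. Two repeats identical to the triggering ECG satisfy the stop rule, although both still show QT of at least 500 ms.

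**Step 3: QTcF above 500 ms on triplicate ECGs**

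No repeats start if both triggers fail.
- (b) fails when QT < 500 ms, that is HR > 60 × (QTcF/500)^3. At QTcF 505 ms this means HR above 61.8 bpm.
- Once QTcF exceeds 500 ms, the 450 ms part of (a) is met, so (a) fails only if QTcF < baseline + 60 ms.

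The untriggered band is therefore 500 < QTcF < baseline + 60 ms:

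| Baseline QTcF (ms) | Untriggered QTcF (ms) |
|---|---|
| 440 or less | none |
| 445 | above 500, below 505 |
| 450 | above 500, below 510 |

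Example: baseline 445 ms, post-dose 503 ms, 75 bpm. The rise is 503 − 445 = 58 ms, so (a) does not fire. QT = 503 × (60/75)^(1/3) = 466.9 ms, so (b) does not fire. Yet 503 ms exceeds the 500 ms limit in 7.1.2 and Appendix 8.

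**Step 4: QTcF above 500 ms on single ECGs**

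Trigger (a) is worded for a triplicate mean, and these visits have none. Read literally, only (b) remains, so any QTcF above 500 ms with QT below 500 ms starts no repeats, whatever the baseline. Example: baseline 420 ms, QTcF 505 ms, 75 bpm, QT 468.8 ms. The rise is 85 ms and would fire (a) on a triplicate; on a single ECG the text does not say that it does.

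**The case against.** The strongest reply is that the protocol already covers most of this, and much of that stands. Trigger (a) is on QTcF and catches every triplicate mean above 500 ms when baseline is 440 ms or less. Section 7.1.2 does more than withdraw treatment: for a clinically significant finding the investigator must decide on continuation and on any change in management, document the ECG review, and report a new relevant finding as an AE. That applies equally after a single dose. Appendix 8 findings are recommended as alerts, and 8.3 allows unscheduled measurements at any time. What remains is that none of these provisions mandates the hourly repeats. The withdrawal criterion in 7.1.2 is also worded for a triplicate average, so its reach at single-ECG visits is unclear too.

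Uncorrected QT in trigger (b) may also be deliberate, since QT above 500 ms is tabulated in its own right. That is a fair reading of the trigger, but it does not explain stopping a QT trigger on QTcF.

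A reader might infer that a triggered ECG releases the participant at once. It does not: two successive ECGs are required. In the 50 bpm example QTcF is 471 ms, below the 500 ms limit used elsewhere, so that case shows an incoherent stop rule and not a missed QTcF above 500 ms.

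**Conclusion.** The mismatch is real and unreconciled, and its reach is limited. Below 60 bpm, the stop rule after trigger (b) can be met by ECGs that still meet the trigger. Above 60 bpm, a QTcF over 500 ms can fail to start the mandatory repeats. On triplicates this needs a baseline above 440 ms and, for baselines up to 450 ms, lies between 500 and 510 ms. At single-ECG visits the gap has no baseline limit if trigger (a) is read literally.

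A reader might infer that the protocol overlooks QTcF above 500 ms generally, or that all ECG rules must share one threshold. The documents support neither. Trigger (a), investigator review and the alerts cover much of the ground, and graded limits (Appendix 8 itself uses 480 and 500 ms) are not a contradiction.

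The sizes rest on assumed heart rates and on the screening limit holding at the Day 1 baseline; a higher baseline widens the triplicate band. How many participants would fall in the gap cannot be estimated from the documents. The planned QT and QTcF tables are defined separately from the triggers, so their categories are not affected.

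**What to change.** Reconcile Protocol 8.3.3 with 7.1.2, Appendix 8 and the SAP QTcF categories. Two statements are needed:

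- Trigger (b) and the rule that stops the repeats it starts should be expressed in the same interval measure. The continuous-monitoring and cardiologist steps and the closing paragraph of 8.3.3 should be checked against that choice.
- The text should say how trigger (a) applies where only a single ECG is taken.

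If uncorrected QT in (b) is intended, a sentence giving the reason would settle the question. Which measure and thresholds to use is for the sponsor to decide. The cost is amendment wording; no new measurement is needed, because the ECG machine already reports heart rate, QT and QTcF.
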